9.7 Pregnancy

Pregnancy alone is not regarded as an AE unless there is a suspicion that the study drug may have interfered with the effectiveness of a contraceptive medication.

Elective abortions without complications should not be handled as AEs, unless they were therapeutic abortions. Hospitalization for normal delivery of a healthy newborn should not be considered an SAE.

If a pregnancy or a positive pregnancy test is reported for a patient during study participation, the study drug must be immediately discontinued.

Pregnancies occurring during the study until EOS must be reported. All pregnancies must be reported to the Sponsor within 24 hours after becoming aware of the pregnancy, using the initial pregnancy report form. The Investigator should counsel the patient; discuss the risks of continuing with the pregnancy and possible effects on the fetus. The Investigator must follow-up and document the course and outcome of all pregnancies, even if the patient was discontinued from the study or if the study has finished.

All outcomes of pregnancy must be reported by the Investigator to the Sponsor on the pregnancy outcome report form within 30 days after he/she becomes aware of the outcome.

Any SAE that occurs during a pregnancy must be recorded on the SAE report form (e.g. maternal serious complications, spontaneous or therapeutic abortion, ectopic pregnancy, stillbirth, neonatal death, congenital anomaly, or birth defects) and reported in accordance with the procedure for reporting of SAEs.

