Primary Objective: To demonstrate the equivalence in efficacy of LUBT010 to Lucentis® in terms of visual acuity, in patients with Neovascular Age-Related Macular Degeneration.		
Secondary Objectives: 
 • To assess the safety and tolerability of LUBT010 as compared to Lucentis®. • To assess the immunogenicity of LUBT010 as compared to Lucentis® 		
Study Design: Global, Phase III, Double Blind, Randomized Controlled, two-arm, interventional study in patients with neovascular AMD.		
Methodology: Eligible patients with Neovascular AMD will be randomly assigned to receive either LUBT010 0.5 mg (0.05 mL of 10 mg/mL ranibizumab) once monthly (intravitreal injection) or Lucentis® 0.5 mg (0.05 mL of 10 mg/mL ranibizumab) once monthly (intravitreal injection) for 12 months. Patients will be randomized on Day 1. Only one eye per patient will receive the investigational product (IP). Patients will visit site for a safety visit after the first dose on any day from Day 2 to Day 9, followed by the next visit on Day 31 ± 2 days, and thereafter monthly for a total of 12 months (i.e. Day 61, Day 91, Day 121, Day 151, Day 181, Day 211, Day 241, Day 271, Day 301, Day 331, and Day 360), with an allowable visit window period of ± 2 days. A post injection visit/ telephonic safety assessment after every injection will be done as deemed necessary by Investigator. Efficacy, safety, and immunogenicity assessments will be done periodically. Day 360 ± 2 will be End of Study (EOS) visit.		
Number of Patients: Adequate number of patients will be screened to randomize approximately 600 patients to 2 treatment arms in 1:1 ratio to have approximately 558 evaluable patients.		
Diagnosis and Main Criteria for Inclusion: Ambulatory male and female patients aged ≥50 years with active choroidal neovascularization (CNV) lesions involving the foveal center secondary to neovascular AMD, who are anti-VEGF naïve and having best corrected visual acuity (BCVA) in the study eye between 20/40 and 20/200 (Snellen equivalent), using Early Treatment Diabetic Retinopathy Study (ETDRS) chart testing.		
Investigational Product: The IPs will be supplied as: Test Product: LUBT010 supplied as single-use, 2-cc glass vial containing 2.3 mg of ranibizumab in 0.23 mL solution designed to deliver 0.05 mL of 10 mg/mL ranibizumab, by intravitreal injection.		

Name of Sponsor/Company: Lupin	Protocol No.: LRP/LUBT010/2016/008	
Name of Active Ingredient: Ranibizumab		

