- 13 To be performed pre-treatment
- 14 Predose (both eyes) & Post dose (study eye only)
- 15 Measurement method used for a patient to be preferably consistent throughout the study
- 16 Obtained pre-treatment for both eyes and 60 min (\pm 30 min) post injection for study eye only
- 17 Fundus photographs/ soft copy to be retained as source document
- 18 Known history of sensitivity to fluorescein dye to be checked before Fluorescein angiography
- 19 To be done in both eyes at screening and in study eye after every injection within a month unless not considered necessary by PI as decided by clinical examination.
- 20 Blood samples for immunogenicity to be collected, before dosing study drug (predose) at Day 1, Day 31, Day 91, Day 181, Day 271, and at EOS visit (Day 360).
- 21 In case of early discontinuations/ premature termination of the study all EOS investigations should be done on the day of termination as far as possible.

Figure 1: Study Flow Chart

- o D = Day
- o  - Lucentis® or LUBT010 injection to be given intravitreally for 12 months at following monthly visits: D1, D31, D61, D91, D121, D151, D181, D211, D241, D271, D301, and D331 with an allowable visit window period of \pm 2 days.
- o Patients will visit site for a safety visit after the first dose on any day during Day 2 to 9. A post injection visit/ telephonic safety assessment after every injection will be done as deemed necessary by Investigator. Day 331 will be the End of Treatment (EOT) visit and Day 360 will be the End of Study (EOS)visit.
- o Efficacy & Safety assessments will be done at monthly visits. Immunogenicity testing will be done at Day 1 and at the end of 1 month (D31), 3 months (D91), 6 months (D181), 9 months (D271), and 12 months (D360).

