No special dosage modification is required for any of the populations that have been studied (e.g., gender, elderly or renal impairment status). The systemic exposures are very low after ocular administration, but due to its mechanism of action, ranibizumab is regarded as potentially teratogenic and embryo-/fetotoxic and must not be used in pregnant and lactating women unless absolutely needed due to the potential risk to the fetus. Women of childbearing potential should use effective contraception during treatment. Safety has not been established in nursing women or pediatric patients; breast-feeding is not recommended during the use of ranibizumab.

The most frequently reported ocular adverse reactions following injection of Lucentis® are eye pain, ocular hyperemia, increased intraocular pressure, vitritis, vitreous detachment, retinal hemorrhage, visual disturbance, vitreous floaters, conjunctival hemorrhage, eye irritation, foreign body sensation in eyes, increased lacrimation, blepharitis, dry eye and eye pruritus. The most frequently reported non-ocular adverse reactions are headache, nasopharyngitis and arthralgia.

Less frequently reported, but more serious, adverse reactions include endophthalmitis, blindness, retinal detachment, retinal tear and iatrogenic traumatic cataract.

The investigational biosimilar of Lupin is also supplied as a single-use, 2-cc glass vial containing 2.3 mg of ranibizumab in 0.23 mL designed to deliver 0.05 mL of 10 mg/mL ranibizumab, by intravitreal injection. The PCT study that has been conducted with LUBT010 includes the repeated dose (4-week) intravitreal toxicity study in rabbit with 14-day recovery period.

Pre-clinical program of Lupin's biosimilar ranibizumab revealed that it is safe and well tolerated when given intravitreally. Moreover, it is also well tolerated at the site of injections. Lupin has demonstrated analytical, functional and *in vivo* nonclinical similarity to Lucentis®. Therefore, Lupin intends to take this product forward in the clinical development.

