6.4 Selection of Study Population**6.4.1 Inclusion Criteria**

Patients satisfying all of the following criteria will be included in the study:

1. Ambulatory male or female participants with age \geq 50 years at the time of screening who are capable of understanding and giving written informed consent.

2. Primary or recurrent (anti-VEGF naïve) active CNV[®] lesions involving the foveal center secondary to AMD in any one of the eyes.
3. BCVA in the study eye, using ETDRS testing, between 20/40 and 20/200 (Snellen equivalent), both inclusive, before pupil dilation.
4. Willingness and ability to undertake all scheduled visits and assessments.
5. Females, who are of non-child bearing potential (surgically sterile or menopausal), OR, if of child bearing potential using effective birth control measures and non-pregnant and non-lactating during the study and 3 months after the last dose (Refer Section 2 - Definition of Terms).

[®]Active CNV is defined as any leakage detected on FA

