6.4.5 Other Patient Restrictions

Patients may not participate in another clinical study that involves an investigational product (IP) during this study.

Females patient currently pregnant or breast feeding or planning to conceive are not allowed to be included in the study. Female patients should refrain from becoming pregnant during the study period and should use effective contraception during the study and 3 months after the last dose of study drug.

For concomitant medications/treatments which are restricted during the study, please see Section 7.1.6.

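### Section 9.7 ends pregnancy reporting at EOS, about 29 days after the last injection, so roughly two thirds of the protocol's 3-month post-dose contraception period has no clear reporting duty

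*Combined protocol and SAP*

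**What the plan says.** Section 9.7 fixes the reporting period: "Pregnancies occurring during the study until EOS must be reported". It then gives a 24-hour deadline for notifying the sponsor once a pregnancy is known. It also asks the investigator to follow pregnancies to outcome, including after a patient has left or the study has ended.

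The timing comes from the notes to the study flow chart (Figure 1): "Day 331 will be the End of Treatment (EOT) visit and Day 360 will be the End of Study (EOS)visit". The synopsis states the monthly schedule "with an allowable visit window period of ± 2 days".

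Two sections set a longer post-dose period for women of childbearing potential:
- Section 6.4.1, criterion 5, requires "effective birth control measures and non-pregnant and non-lactating during the study and 3 months after the last dose".
- Section 6.4.5 says that female patients "should use effective contraception during the study and 3 months after the last dose of study drug".

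Section 3.2 gives the reason for caution: "ranibizumab is regarded as potentially teratogenic and embryo-/fetotoxic". The same paragraph describes a shorter contraception period: "Women of childbearing potential should use effective contraception during treatment".

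Three other provisions bear on the point. SAE reporting (9.1.3.3) ends at the Day 360 visit. The last scheduled pregnancy test (9.6) is at EOS. For a patient who stops early, section 6.4.3 places the EOS investigations on the day of termination, as far as that is possible.

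**The concern.** The protocol asks women of childbearing potential to avoid pregnancy for 3 months after the last dose but asks sites to report pregnancies only until EOS, which comes about one month after it. A pregnancy that begins between those two dates falls inside a period the protocol thought worth guarding, yet no section clearly requires it to be reported or provides for finding it. The SAE route does not clearly fill the gap, because it closes on the same day and section 9.7 does not treat pregnancy alone as an AE.

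What is at stake is completeness of safety information. Such a case might not reach the sponsor or be followed to outcome, and for LUBT010 itself the protocol describes only analytical and pre-clinical data so far. Efficacy conclusions are not affected.

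**Working it through.** The documents state no figure for this gap, so there is nothing to reproduce. The check is day arithmetic.

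**Inputs**
- Last injection: Day 331 (Figure 1 notes).
- EOS: Day 360 (same place).
- Visit window: ± 2 days at each visit (synopsis).
- Post-dose contraception period: 3 months after the last dose (6.4.1 criterion 5; 6.4.5). The protocol does not convert this to days; I assume 90 to 92.

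**Step 1. Last dose to end of reporting, completers**
- Nominal: 360 − 331 = 29 days.
- Shortest: 358 − 333 = 25 days.
- Longest: 362 − 329 = 33 days.

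**Step 2. Uncovered part = contraception period − gap**

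| 3 months taken as | Gap 29 days | Gap 33 days | Gap 25 days |
|---|---|---|---|
| 90 days | 61 (67.8%) | 57 (63.3%) | 65 (72.2%) |
| 92 days | 63 (68.5%) | 59 (64.1%) | 67 (72.8%) |

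On the nominal schedule, about 68% of the period is uncovered. The visit windows widen this to 63% to 73%.

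**Step 3. Does other text in 9.7 or elsewhere close the gap?**
- The 24-hour sentence has no end date of its own. It directly follows the sentence that ends the period at EOS, and it sets how fast to report rather than for how long. A broader reading is possible, so the text is ambiguous.
- The follow-up sentence concerns the course and outcome of pregnancies after the study. It provides no means of identifying one that starts after EOS.
- SAE reporting ends at Day 360, and no pregnancy test or patient contact is scheduled after EOS.

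**Step 4. Early discontinuation**

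If EOS is taken to be the termination visit, the reporting period closes on that day. Where that is fewer than 29 days after the last injection, the uncovered part exceeds the completers' figure. The documents do not allow a single number here.

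**Step 5. After the change in 9.7**

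Reporting would run to Day 331 + 90 to 92 = Day 421 to 423, which is 61 to 63 days past Day 360. The uncovered share would fall to 0%.

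**The case against.** The strongest reply is that a contraception period and a reporting period are different requirements and need not be equally long. A reader might infer that the protocol declares fetal risk to last 3 months and then contradicts itself. The documents do not support that. No section says how long fetal risk lasts, and section 3.2, which makes the teratogenicity statement, speaks of contraception only during treatment. What stands is a mismatch with a required contraception period.

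A reader might also take two thirds of the days as two thirds of the risk. Section 3.2 gives a half-life of about 9 days. Assuming simple exponential decline, 2^(−29/9), or about 11%, of the post-dose level remains 29 days after the last dose. The stated steady-state minimum of 0.22 ng/mL is 50-fold below the lower end of the 11 to 27 ng/mL range for half-inhibition of VEGF-A (11 / 0.22 = 50). The uncovered days are the low-exposure tail, so the percentage measures calendar time only.

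It would also be too strong to say that every such pregnancy would be missed. The 24-hour sentence can be read as open-ended, and nothing stops an investigator from reporting a later case. The consent form and the Safety Monitoring Plan are not among the documents reviewed. Section 9.1.3.5 assigns that plan SAEs, significant AEs and SUSARs and does not mention pregnancy, but women may be told elsewhere to report.

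Finally, one could argue that an early stopper might have almost the whole 3 months uncovered. That needs termination on an injection day, plus a reading of section 6.4.3 under which the reporting period, and not just the EOS assessments, moves to that day. The text does not clearly say so.

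These replies limit the claim. None of them supplies a clear reporting duty or planned ascertainment after EOS.

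**Conclusion.** The point holds as a minor inconsistency in safety reporting. For completers, 61 to 63 of the 90 to 92 days in the protocol's own post-dose contraception period (about 68%; 63% to 73% with visit windows) lie beyond the reporting period in 9.7. The uncovered part may be longer after early discontinuation. The text of 9.7 is at best ambiguous about a pregnancy that begins after EOS.

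This rests on two assumptions: that 3 months means 90 to 92 days, and that the 24-hour sentence is read together with the EOS limit that precedes it. Few patients are likely to be affected, since entry age is 50 or over; the documents do not give the number of women of childbearing potential. The primary endpoint and its analysis do not depend on this.

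**What to change.** In section 9.7, replace the EOS limit so that the pregnancy reporting period matches the post-dose contraception period already set in 6.4.1 criterion 5 and 6.4.5. Count it from the last dose of study drug, and state that it applies to patients who discontinue early. Make clear that the 24-hour deadline applies throughout that period. At EOS or discontinuation, tell women of childbearing potential to report a pregnancy that occurs within it.

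Section 3.2, which mentions contraception only during treatment, should be reconciled with 6.4.1, 6.4.5 and 9.7 so that the protocol carries one consistent period. Which period is appropriate is for the sponsor to settle.

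The cost is a small text change and a few site contacts after EOS for what is likely to be a small group. No dose, visit or analysis changes.

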10 ASSESSMENT OF IMMUNOGENICITY

10.1 Anti-Drug Antibodies

Immunogenicity will be assessed in patients on Day 1 (pre-dose) and thereafter as per Table 1. Samples for immunogenicity will be collected prior to dosing. An appropriate and validated method will be used for assessment of anti-drug antibodies.

Note: A tiered approach will be followed for assessing antibody formation in response to IP administration. All samples will be screened for occurrence of binding antibodies. Samples that test positive will be subjected to a confirmatory assay. Samples that are positive on confirmatory assay will further be tested for assessing the titer and neutralizing potential.

10.1.1 Collection, Handling, and Analysis of Immunogenicity Samples

Blood samples will be collected using a blood collection tube by venipuncture.

Anti-drug antibodies will be analyzed using a validated method, at a laboratory designated for analysis of immunogenicity samples.

The sample handling, transportation, storage, and processing of will be carried out according to Laboratory Manual.

[figure not shown]
11 STATISTICAL EVALUATION

11.1 Sample Size and Power

Sample Size for Change from Baseline in BCVA at Month 12 (Primary Endpoint)

In order to determine the margin for equivalence, a meta-analysis based on current literature in AMD patients was performed. Data included were data from the 0.5 mg ranibizumab and the SHAM treatment groups. Studies included were in the original regulatory filing. Change from baseline to Month 12 of BCVA was used as the endpoint. A mean difference of 17.9 letters [95% CI 15.7-20.0] was found. Heterogeneity was assessed and was not found to be statistically significant ($p=0.5752$), and hence the fixed-effect model was used to construct the confidence interval. Based on a lower confidence bound of 15.7 letters, an equivalence margin of 4 letters preserved 74.5% of the treatment effect. The pooled standard deviation (SD) from the ranibizumab arms is 14.5 letters.

Figure 2: Meta-Analysis

A sample size of 558 evaluable patients allocated in 1:1 ratio (279 per treatment) at (two-sided) 5% level of significance and 80% power will be required to test the therapeutic equivalence between Lupin's LUBT010 verses Lucentis® at equivalence margin of 4 letters and SD of 14.5 letters.

Sample Size

Assuming a dropout rate of 7%, 600 patients will be randomized so as get approximately 558 evaluable patients in a 1:1 ratio between the two treatment arms (279 in each arm) to yield 80% power for the mean change from baseline in BCVA at the end of 12 months.

11.2 Statistical Methods

This section describes the statistical analysis as it is foreseen at the time of planning the study. Any major deviations from this plan, the reasons for such deviations, and all alternative or additional statistical analyses will be provided in a Statistical Analysis Plan (SAP) as applicable.

Continuous variables will be presented in summary statistics of number of patients (n), mean, SD, median, minimum and maximum by appropriate group and time point. Categorical variables will be described using the frequency count of the events, and the number and proportion of responding patients.

The study being conducted at multiple sites, the data collected from individual sites will be pooled for analysis. Detailed listings will be produced for all relevant efficacy, safety, and immunogenicity data by treatment and by visits wherever applicable.

Detailed methodology on summary and statistical analysis of the data collected in this study will be provided in the SAP which will be finalized prior to the database lock.

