6 INVESTIGATIONAL PLAN

6.1 Overall Study Design and Plan

This is a global, Phase III, double blind, randomized, controlled clinical study. The objective of the study is to compare the efficacy, safety and immunogenicity of LUBT010 to that of Lucentis® in patients with neovascular AMD.

Approximately 75 –100 sites across Europe, US, and India, having ophthalmologists who are experienced in diagnosing and treating neovascular AMD, and where adequate facilities for conduct of trial are available will be selected for the study. Study will be initiated only after receipt of regulatory and EC approval. Screening investigations on patient will be done only after signing of written informed consent. Adequate number of patients will be screened to randomize approximately 600 patients to have 558 evaluable patients in the study. (Note: Every attempt will be made to ensure at least 25% of patients enrolled are with light colored irises).

Patients will be randomized on Day 1. Total 12 injections (Lucentis® or LUBT010 0.5 mg intravitreal injection, once monthly) would be given to each patient during the study. The duration of the treatment and assessments will be 12 months during which the efficacy, safety and immunogenicity assessments will be done. The total study duration for each patient would be around 13 months. It would include up to 28 days of screening period and 12 months of treatment and assessment period.

The trial consists of following parts:

- Screening Period (maximum 28 days)
- Treatment and Assessment Period (12 months)
 - Day 1 (Randomization and first dose of ranibizumab)
 - Safety Visit: Day 2 to 9 (on any day from Day 2 to Day 9)
 - Treatment visits (\pm 2 days): Day 31 (second dose), and thereafter monthly for a total of 12 months (i.e. Day 61, Day 91, Day 121, Day 151, Day 181, Day 211, Day 241, Day 271, Day 301, and Day 331) followed by post-injection visit/Telephonic Follow-Up, as deemed necessary by Investigator.
 - Day 360 (\pm 2 days) - End of Study (EOS)

After signing the informed consent form, the patients will undergo screening assessments to confirm eligibility. These include demographics, medical and surgical history, (including ophthalmic history), weight, ECG, vital signs, physical, systemic and ophthalmic examination, and laboratory assessments (blood and urine) as given in Table 1.

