6.3.1.1 Screening Visit (Maximum 28 days)

Screening procedures are as follows:

- Obtain written informed consent as per regulatory requirement
- Record demographic data (age, gender, race/ethnicity)
- Record medical and surgical history (including ophthalmic history)
- Record concomitant medications/treatment.
- Vital signs assessment (temperature, Pulse, blood pressure [BP], respiratory rate [RR])
- Perform physical and systemic examination
- Record weight
- Perform ECG
- AE assessment
- Perform clinical laboratory assessment (hematology, biochemistry, and urinalysis) (and any other investigation, if deemed necessary by investigator)
- Assessment of serological tests[#] for: human immunodeficiency virus (HIV), Hepatitis B virus (HBsAg), Hepatitis C virus (HCV), and syphilis (Rapid Plasma Reagins [RPR] test).
- Follicle stimulating hormone (FSH) to be done in all females at screening.

Perform serum pregnancy test in females of childbearing potential (females who are not surgically sterile or menopausal).

- Ophthalmic Examinations[@]: Unless otherwise stated these will be done for both the eyes

- Refraction assessment
- BCVA by ETDRS chart*
- Ophthalmoscopy examination (indirect dilated)
- Slit lamp examination
- Intraocular pressure (IOP) measurement
- Fluorescein angiography (FA)[#]: History of sensitivity to fluorescein dye to be checked before FA
- OCT[#]

@ Refraction and visual acuity testing should be done before pupil dilation and prior to other ophthalmic investigations. Only when the patient is eligible based on BCVA, the remaining investigations should be done. The order in which various procedures are performed may vary from clinic to clinic, provided the procedures are completed within screening period.

The period of 28 days can be relaxed up to two months for the tests marked # considering the longevity of the results for patients who may undergo rescreening (see Section 6.4.4).

* BCVA measurements should begin in a sitting position using ETDRS chart (original Sloan letter chart or number chart) at a starting distance of 4 meters (for a subject, the same ETDRS chart used at screening should be used for all subsequent visit). A standardized ETDRS chart must be used at all participating sites to minimize the assessment discrepancy. Visual acuity measurements for each eye should be obtained by an ophthalmologist or a certified examiner.

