6.4.2 Exclusion Criteria

Patients who meet any of the following criteria should be disqualified from entering the study:

1. Known hypersensitivity to ranibizumab or any of the components of study medication.
2. Known history of allergy to fluorescein dye.
3. Scar, fibrosis, or atrophy involving the center of the fovea in the study eye as assessed by FA (confirmed by independent central reading center).
4. Subretinal hemorrhage in the study eye that involves the center of the fovea, the size of the hemorrhage is either $\geq 50\%$ of the total lesion area or ≥ 1 -disc area in size (confirmed by independent central reading center).
5. Total lesion area ≥ 12.0 -disc areas (DA) in size (including blood, scars, and neovascularization) as assessed by FA in the study eye (confirmed by independent central reading center).
6. History of vitrectomy, submacular surgery, or other surgical intervention for AMD in the study eye.
7. Employees of clinical study sites, individuals directly involved with the conduct of the study or immediate family members thereof, prisoners, and persons who are legally institutionalized.
8. Any other pathology involving the CNV lesion like retro-foveolar atrophy or permanent structural damage to fovea or fibrosis/ hemorrhage involving fovea $> 50\%$ of lesion area of study eye that can affect the efficacy of drug.
9. Vitreous hemorrhage or history of rhegmatogenous retinal detachment, retinal pigment epithelial tears or rips involving the macula or macular hole (stage 1 to 4) in the study eye as assessed by FA (confirmed by independent central reading center).
10. Uncontrolled glaucoma as evident by progressive damage to optic nerve or visual fields despite optimum therapy; or steroid-induced glaucoma with continued use of steroids that requires IOP-lowering treatment.
11. History of serious complications following surgery in the study eye within 1 year prior to randomization.
12. Previous treatment with intravenous or intravitreal anti-VEGF agents such as Bevacizumab, Ranibizumab, Aflibercept, Pegaptanib, Brolucizumab in either of the eyes.
13. Previous external beam radiation or any laser therapy photocoagulation/ thermal laser thermotherapy/verteporfin photodynamic therapy (PDT) involving the foveal center in the study eye within 5 years prior to randomization.

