7.1.3 Randomization of Study Treatments

The treatment arm (test or reference) for each patient during the study will be assigned according to randomization list. This randomization list will be prepared reviewed and finalized in a blinded manner and will not be accessible to the study team involved in the study conduct. The treatment will be assigned at the time of randomization, after confirming patient's

eligibility. Patients will be randomized in a 1:1 ratio to either LUBT010 or Lucentis®. Patients who qualify for study randomization will have a unique randomization number. Randomization will be stratified by iris color (light colored, not light colored) to maintain treatment balance within strata. Randomization block size will be specified in the randomization plan and will not be shared with investigators. After completion of required number (600 patients), some patients who qualify in screening may not be enrolled in the study.

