11.7 Efficacy Analysis

11.7.1 Primary Efficacy Endpoint

The primary endpoint is mean change in BCVA from baseline in the study eye at the end of 12 months, assessed with the ETDRS chart.

The primary endpoint will be analyzed using ANCOVA model with fixed-effect treatment, and baseline BCVA as covariate.

Denote the population parameter for the mean change from baseline in BCVA by θ_R for LUBT010 arm, and by θ_L for Lucentis® arm, expressed in letters. The hypothesis to be tested will be

$$H_0: \theta_R - \theta_L \leq -4 \text{ or } 4 \leq \theta_R - \theta_L \text{ versus } H_A: -4 < \theta_R - \theta_L < 4.$$

The hypothesis will be tested using the two-sided 90% confidence interval for the difference as accepted by US FDA. If the 90% confidence interval lies wholly between -4 and 4, then the

null hypothesis will be rejected. The confidence interval will be constructed using a two-sample t-test.

Similar methodology will be used with 95% CI of mean difference for EMA. Thus, if 95% (2-sided) confidence interval, lies wholly within the equivalence margin (-4, 4), then the null hypothesis will be rejected.

Missing data in the primary endpoint will be imputed by multiple imputation approach under the assumption of outcome is Missing At Random (MAR). The MAR assumption will be implemented using ANCOVA model by repeated imputation of missing values in primary endpoint. For this assumption, missing outcomes are modeled using observations from a patient's own treatment arm. Thus, MAR would tend to reflect in the missing data any observed differences between treatment groups and is appropriately conservative for the objective of assessing equivalence. Then, to assess the robustness of MAR assumption in primary analysis, the sensitivity analysis via tipping point approach under the Missing Not At Random (MNAR) assumption will be performed.

Details will be provided in the SAP, which will be finalized and signed prior to database lock and unblinding

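### The primary ANCOVA adjusts only for baseline BCVA: region, age and the stratification factor iris color are left out, which may forgo some precision, and no regional summary is pre-specified in the protocol text.

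*Combined protocol and SAP*

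**What the plan says.** - **Setting.** Section 6.1 plans about 75 to 100 "sites across Europe, US, and India", with about 600 patients randomized.
- **Pooling.** Section 11.2: "The study being conducted at multiple sites, the data collected from individual sites will be pooled for analysis".
- **Primary model.** Section 11.7.1: "The primary endpoint will be analyzed using ANCOVA model with fixed-effect treatment, and baseline BCVA as covariate". The synopsis gives the same terms.
- **Decision interval.** Section 11.7.1 also says: "The confidence interval will be constructed using a two-sample t-test". Two intervals are specified against ±4 letters: 90% for the FDA and 95% for the EMA (sections 11.2.2 and 11.7.1).
- **Stratification.** Section 7.1.3: "Randomization will be stratified by iris color (light colored, not light colored) to maintain treatment balance within strata". Region is not a stratification factor.
- **Baseline data.** Section 6.3.1.1 lists "Record demographic data (age, gender, race/ethnicity" among the screening procedures. Lesion area appears in section 6.4.2 as an exclusion threshold, "as assessed by FA in the study eye (confirmed by independent central reading center".
- **Missing data.** Month-12 values are imputed under MAR with an ANCOVA model and the patient's own arm (section 11.7.1).
- **Deferral.** Section 11.2 leaves additional analyses and detailed methods to a SAP to be finalized before database lock. No separate SAP text is in the document.

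**The concern.** An equivalence decision depends on the width of the interval. If 12-month BCVA change varies with region, age or iris color beyond what baseline BCVA explains, that variation stays in the residual and widens both intervals relative to ±4 letters. Adjustment would remove it without adding a patient.

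The design gives reasons to consider these terms:
- Iris color was used to balance the arms but is not in the analysis model.
- Region may affect the outcome or the missingness. Two ETDRS chart types are allowed (sections 6.3.1.1 and 8.2), ranibizumab for the fellow eye depends on the product approved in each country (section 7.1.6), and the protocol expects to keep assessing pandemic impact (section 3.4.1). If missingness and outcome both vary by region, MAR is more plausible with region in the imputation model.
- The result is meant for the US, EU and Indian markets (section 3.1), so regional estimates are likely to be asked for. A table planned in advance is easier to defend than a regional cut made after unblinding.

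**Working it through.** **Inputs from section 11.1:** SD 14.5 letters, margin 4 letters, 279 evaluable per arm, two-sided 5%, 80% power, 7% dropout. **Assumed, because not stated:** true difference 0.

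**1. Reproduce the plan's figure.** Two one-sided tests at 2.5% each (the 95% rule), normal approximation:

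n per arm = 2 × [14.5 × (1.960 + 1.282) / 4]² = 276.1, so 277.

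The t-based calculation gives 278 per arm, against 279 stated. Power at 279 per arm is 80.4%. With dropout, 558 / 0.93 = 600. The sample size reproduces, and it relies on no covariate.

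**2. Effect of added covariates.** The documents do not say how much variance region, age and iris color explain beyond baseline BCVA, so a range is assumed. With R² the share of residual variance removed:

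- residual SD = 14.5 × √(1 − R²)
- SE = residual SD × √(2/279)
- half-width = t × SE, with 556 df

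| R² (assumed) | Residual SD | 95% half-width | Power, 95% rule | Power, 90% rule |
|---|---|---|---|---|
| 0 | 14.50 | 2.41 | 80.4% | 89.2% |
| 2% | 14.35 | 2.39 | 81.5% | 89.9% |
| 5% | 14.13 | 2.35 | 83.2% | 91.0% |
| 10% | 13.76 | 2.29 | 85.8% | 92.6% |

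The SE falls by 1 − √0.98 = 1.0% at the low end and 1 − √0.90 = 5.1% at the high end.

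**3. Credit for baseline BCVA.** Step 2 starts from 14.5, the pooled SD of the ranibizumab arms, and gives the planned baseline adjustment no credit. Suppose baseline BCVA alone removed 10% of variance (an assumption). Power under the 95% rule is then already 85.8%. Removing a further 2% to 10% of what remains gives SD 14.5 × √(0.90 × 0.98) = 13.62 to 14.5 × √(0.90 × 0.90) = 13.05, and power 86.7% to 90.2%. The gain is 0.9 to 4.4 points, instead of 1.1 to 5.4.

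**4. What a regional table can show.** Assume three equal regions, 279 / 3 = 93 per arm each:

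- 95% half-width within a region = 1.96 × 14.5 × √(2/93) = 4.2 letters, wider than the margin
- SE of the difference between two regional treatment differences = 14.5 × √(4/93) = 3.0 letters
- a 2-df interaction test at 5% has about 26% power if one region differs from the others by 4 letters

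**5. Region rather than site.** 600 / 100 = 6 to 600 / 75 = 8 randomized patients per site. Fixed site effects are impractical; three regions are not.

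**6. Which interval decides.** A two-sample t-test interval uses no covariate, not even baseline BCVA. While that sentence stands, adding terms to the ANCOVA need not change the decision interval, and the gain in step 2 could be lost.

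**The case against.** The best defense is that nothing is broken. The comparison is randomized, so leaving out prognostic factors does not bias it. Chance regional imbalance is already reflected in the interval, and 80% power is met without these terms. The gain rests on an assumed R² and could be about one point. Analyzing multi-site data together is normal and, at 6 to 8 patients per site, unavoidable. All of this stands.

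Deferral to the SAP is a weaker defense. It covers additional analyses, but the terms of the primary model are already stated, in the synopsis and in section 11.7.1. Adding covariates later would change a stated primary model.

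A reader might infer several stronger things that the documents do not support:

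- **Pooling is itself an error.** The sentence rules out neither a region term nor a regional summary.
- **No regional check will exist.** None is pre-specified in the protocol text; a separate SAP may contain one.
- **A single interval serves every authority.** Two are specified, 90% and 95%.
- **Lesion area is a recorded covariate left unused.** The text describes a centrally confirmed eligibility threshold. It does not say that a numeric area is kept for analysis.
- **A regional table would show whether the difference is the same everywhere.** At about ±4.2 letters per region it could neither establish nor exclude that.

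**Conclusion.** The point holds as a low-cost improvement to the analysis; it is not a flaw in validity or sample size. Region, age and iris color are available and missing from the primary model. Including them would raise power under the 95% rule by roughly 1 to 5 points, on the assumptions that they remove 2% to 10% of residual variance, that the true difference is 0, and that the SD is 14.5 letters with 279 per arm. The gain is slightly smaller once baseline BCVA is credited, and it could be negligible if the factors are only weakly prognostic. It is secured only if the decision intervals come from the ANCOVA. The absence of a planned regional summary is a lesser, descriptive gap, and the ±4.2 letters depends on the assumption of equal regions.

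**What to change.** Before unblinding:

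1. In section 11.7.1 and the synopsis, specify ANCOVA with treatment, baseline BCVA, region (Europe/US/India), iris color and age. Add reading-center lesion area only if a numeric value is captured.
2. Use the same terms in the multiple-imputation model.
3. Replace the two-sample t-test sentence: both the 90% and the 95% interval should come from this ANCOVA.
4. Add one descriptive table of the adjusted LUBT010 minus Lucentis difference with 95% CI by region. State that these intervals (about ±4.2 letters if the three regions are equal) are too wide to establish consistency.
5. Keep the pooling sentence in section 11.2 and add a reference to the region term.

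The cost is some protocol and SAP wording and one table, with no extra patients or visits. If lesion area is used, a simple rule for missing baseline values is also needed.
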